2.2. Study Objectives, Endpoints, and Estimands

Туре	Objectives	Endpoints	Estimands
Primary:	Primary:	Primary:	Primary:
Efficacy	To evaluate the effect of ponsegromab compared with placebo on body weight in participants with cancer, cachexia, and elevated concentrations of GDF- 15.	Change from baseline body weight at Week 12.	Estimand 1 (similar to "hypothetical") is the difference between ponsegromab and placebo in mean change from baseline in body weight at Week 12, in participants with cancer, cachexia and elevated concentrations of GDF-15, under the scenario of no discontinuation of study intervention and without the potential confounding effect of prohibited procedures, prohibited medications or participants' non-compliance with dosing.
Secondary:	Secondary:	Secondary:	Secondary:
Efficacy	To evaluate the effect of ponsegromab compared to placebo on physical activity and gait as measured by wearable digital sensors in participants with cancer, cachexia, and elevated concentrations of GDF-15.	Change from baseline in physical activity and gait endpoints measured with remote digital sensors at Week 12: Moderate to vigorous physical activity time; Sedentary activity time; Non-sedentary physical activity time Total vector magnitude Mean activity level during M6min (maximum daily 6 minutes of activity); Mean gait speed; 95th percentile gait speed.	Estimand 2 (similar to "hypothetical") is the difference between ponsegromab and placebo in mean change from baseline in each of the physical activity and gait endpoints at Week 12, in participants with cancer, cachexia and elevated concentrations of GDF-15, under the scenario of no discontinuation of study intervention and without the potential confounding effect of prohibited procedures, prohibited medications or participants' non-compliance with dosing.
Efficacy	To evaluate the effect of ponsegromab compared to placebo on the appetite-related symptoms as measured by FAACT in participants with cancer,	Change from baseline in FAACT sub-scale scores at Week 12: FAACT-ACS; FAACT-5IASS.	Estimand 3 (similar to "hypothetical") is the difference between ponsegromab and placebo in mean change from baseline in each FAACT sub scale score at Week

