5.2.3. Mixed Models Repeated Measures (MMRM) Analysis

The MMRM model will include participant as a random term, and baseline, time (as a factor), baseline-by-time interaction, treatment and treatment-by-time interaction as fixed terms in the model. An unstructured covariance matrix will be fitted to the repeated times within subject (other covariance matrices will be considered if necessary), and the Kenward Roger approximation will be used for estimating degrees of freedom. Additional terms may be fitted in the model (eg, type of therapy [ie, platinum or not], type of cancer), as appropriate.

Least-squares (LS) means (and 90% CIs) and LS mean differences versus placebo (and 90% CIs, and p-values for primary and selected secondary/tertiary endpoints), at each timepoint, will be provided. No adjustments will be made for multiplicity. In addition, profile plots of the LS means and differences (and 90% CIs for both) will be produced over time, with a separate line for each treatment group.

Standard SAS output will be provided to support the statistical summary table for the analysis model but will not be included in the CSR.

Example SAS code is provided in Appendix 4.

Statistical Model Diagnostics

The presence of outliers will be investigated for this model. An outlier will be defined as any response data value with a studentized (conditional) residual greater than 3, or less than 3. A listing will be presented of any participants meeting these criteria and will be included with standard SAS output. The assumptions of normality will be verified graphically using

residual plots. For each fitted model, a set of conditional studentized residual plots will be produced, including residual plot, histogram of normality, quartile-quartile (QQ) plot and summary of fit statistics. The residual plots will not be included in the CSR.

If there are outliers or major deviations from normality, then the effect of these on the conclusions may be investigated through alternative transformations and/or analyses excluding outliers. Justification for any alternative to the planned analysis will be given in the report of the study.

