6.1.1.1. Main Analysis

Absolute values, changes from baseline and percent changes from baseline in body weight will be summarized descriptively by treatment group and timepoint, as described in Section 5.2.1. Tables will include baseline and all post-baseline timepoints. Box and whisker plots (or similar) of absolute values, changes from baseline and percent changes from baseline over time will also be produced, with all treatments on the same plot.

Change from baseline in body weight will be analyzed using an MMRM model as described in Section 5.2.3. All post-treatment dosing timepoints up to Week 12 (ie. Weeks 4, 8 and 12) will be included in the model. Additional terms for type of therapy [i.e. platinum or not] and type of cancer will be fitted in the model. Additional plots of LS means and differences (including 90% CIs for both), for Week 12 only, will be produced over treatment.

A Bayesian E_{max} model, as described in Section 5.2.4, will then be fitted to the Week 12 LSmeans and SEs from the MMRM analysis. This will be used to estimate the treatment effect related to the primary Estimand 1 (as described in Section 2.2.1). If the E_{max} model analysis is not performed, the primary results for the study will be based on the MMRM results at Week 12.

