6.5. Subset Analyses

Additional analyses will be performed on the primary endpoint (change from baseline body weight) to assess the effect of the following two subgroup factors:

- Type of cancer (i.e. NSCLC, PANC or CRC)
- Type of therapy (ie, platinum or not) at randomization [+/- 28 days]
- Screening Roche GDF-15 (dichotomized using < or ≥ overall study median level (or an alternative cut-point, if appropriate))

These analyses will be performed on the censored analysis set, as defined in Section 4.

For each subgroup factor, absolute values, changes from baseline and percent changes from baseline in body weight will be summarized descriptively by subgroup factor, treatment group and timepoint, as described in Section 5.2.1. Tables will include baseline and all post-baseline timepoints.

For each subgroup factor, change from baseline in body weight will be analyzed using an MMRM model, as described in Section 6.1.1.1. Additional terms for the subgroup factor and its interaction with treatment group, time and the treatment-by-time interaction, will be included in the model. Other terms (eg, type of therapy [i.e. platinum or not] and type of cancer; described in Section 6.1.1.1) will be dropped from the model, as appropriate. LS means (and 90% CIs) and mean differences versus placebo (and 90% CIs) will be provided. The p-values for the subgroup interaction terms will be included in the tables, e.g. as a footnote. No adjustments will be made for multiplicity.

If the MMRM model cannot be fitted to the data, or the model is deemed inappropriate, the model may be simplified, or the analysis may not be performed.

Additionally, screening Roche GDF-15 will be plotted vs Week 12 change from baseline body weight using a scatterplot. The plot will include all participants and may be colored/trellised by different cancer types and/or type of therapy.

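### The subgroup interaction p-values in SAP 6.5 are not tied to Week 12: as overall term tests they address the three-visit average interaction or its change over time

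*SAP*

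**What the plan says.** SAP 2.2 defines the primary endpoint as "Change from baseline body weight at Week 12". SAP 6.5 takes that endpoint as its target: "Additional analyses will be performed on the primary endpoint (change from baseline body weight) to assess the effect of the following two subgroup factors". (Three factors are then listed: cancer type, platinum therapy and screening GDF-15.)

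The model is the MMRM of SAP 6.1.1.1: "All post-treatment dosing timepoints up to Week 12 (ie. Weeks 4, 8 and 12) will be included in the model". Its base terms, from SAP 5.2.3, are "baseline, time (as a factor), baseline-by-time interaction, treatment and treatment-by-time interaction as fixed terms in the model". For subgroups, SAP 6.5 adds: "Additional terms for the subgroup factor and its interaction with treatment group, time and the treatment-by-time interaction, will be included in the model". This gives subgroup, subgroup-by-treatment, subgroup-by-time and subgroup-by-treatment-by-time.

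There are two kinds of output. For estimates, SAP 6.5 says "LS means (and 90% CIs) and mean differences versus placebo (and 90% CIs) will be provided", and SAP 5.2.3 has such differences reported for each visit, so Week 12 estimates within each subgroup will exist. For inference on effect modification, the plan is only "The p-values for the subgroup interaction terms will be included in the tables, e.g. as a footnote". No Week 12 interaction contrast is named, and nothing says which term answers the question.

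**The concern.** The question in SAP 6.5 concerns Week 12, but the p-values belong to terms of a three-visit model. When a three-way term with time is present, the overall subgroup-by-treatment test is no longer tied to any one visit. A table could therefore show Week 12 subgroup effects that look different beside an unremarkable interaction p-value, or similar Week 12 effects beside a small one.

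The trial's own rationale raises the question of who benefits. Platinum use is the randomization stratum because it may affect response (Protocol 4.1), platinum-treated patients are named as possibly gaining more (Protocol 4.2), and the screening GDF-15 sample may support a companion diagnostic (Protocol 8.7.1).

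**Working it through.** **Plan's own figure.** The documents give no figure for the interaction tests. The sample-size statement in Protocol 9.5 reproduces. With SD 4.9 kg and 30 against 30 + 39 = 69, SE = 4.9 × √(1/30 + 1/69) = 1.072. For 2.7 kg, 2.7/1.072 − 1.645 = 0.875, which gives power 0.81 against the stated 80% or so. The same SD, effect and 30 completers per arm are used below.

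**What each term tests.** For a given dose and a two-level factor, let θ4, θ8 and θ12 be the between-subgroup differences in the dose-versus-placebo effect at the three visits. Let θ̄ = (θ4 + θ8 + θ12)/3.

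- Subgroup-by-treatment (Type III, 3 df): θ̄ = 0 for all three doses.
- Three-way (6 df): θ4 = θ8 = θ12 for all three doses.
- Subgroup-by-time (2 df): subgroup trajectories averaged over arms, which is not a treatment effect.
- The question asked: θ12 = 0 for all three doses (3 df).

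Since θ12 = θ̄ + (θ12 − θ̄), the Week 12 hypothesis needs both treatment-related terms together. A rank check agrees: adding the Week 12 contrasts raises the rank from 3 to 6 for the first term and from 6 to 9 for the second, but leaves the two terms jointly at 9. No joint test is planned.

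**Size, as an illustration.**

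- From Protocol 9.5: 30 completers per arm, Week 12 SD 4.9 kg. The 2.7 kg is borrowed as the interaction size.
- Assumed, not in the documents: a 50:50 split (15 per arm per subgroup), SDs of 2.8 and 4.0 kg at Weeks 4 and 8, AR(1) correlation 0.8, the same interaction in every dose, and a two-sided 10% level to match the 90% CIs.

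The variance of the three-visit average is [2.8² + 4.0² + 4.9² + 2(0.8×2.8×4.0 + 0.8×4.0×4.9 + 0.64×2.8×4.9)]/9 = 12.74, so its SD is 3.57 kg.

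For a 3-df test of a common interaction δ, the noncentrality is λ = 0.75 δ² / (2σ²/15), where 0.75 = 3/(1 + 3) allows for the shared placebo arm.

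- Week 12 contrast: 0.75 × 2.7² / (2 × 24.01/15) = 1.71, power 0.27.
- Averaged term, linear growth (δ = 1.8): 0.75 × 1.8² / (2 × 12.74/15) = 1.43, power 0.24.
- Averaged term, Week 12 only (δ = 0.9): 0.75 × 0.9² / (2 × 12.74/15) = 0.36, power 0.13.

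The three-way column uses the same covariance matrix with 6 df.

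| Interaction at Weeks 4 / 8 / 12 (kg) | Week 12 contrast | Subgroup-by-treatment term | Three-way term |
|---|---|---|---|
| 0.9 / 1.8 / 2.7 (linear) | 0.27 | 0.24 | 0.19 |
| 0 / 0 / 2.7 (Week 12 only) | 0.27 | 0.13 | 0.44 |
| 2.7 / 2.7 / 2.7 (constant) | 0.27 | 0.41 | 0.10 |
| −2.7 / 0 / 2.7 (reverses) | 0.27 | 0.10 | 0.83 |
| 2.7 / 2.7 / 0 (early only) | 0.10 | 0.24 | 0.44 |

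Across all the assumptions tried (correlation 0.6 or 0.8, rising or constant SD, 50:50 or 70:30 split), the Week 12 contrast has power 0.24–0.27 in the first four rows. The averaged term has 0.17–0.27 for linear growth and 0.12–0.14 for Week 12 only. In the early-only row the two terms reject with probability 0.17–0.27 and 0.25–0.44.

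**The case against.** Four points on the other side have force.

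- **The test type is not stated.** The example MMRM code in SAP Appendix 4 is not in the text available, and that absence is not held against the plan. Coefficient p-values with Week 12 as the reference visit would refer to Week 12. They would be one p-value per coefficient rather than per term, though, so the natural reading of the sentence is still the overall term test. The point remains conditional on it.
- **Power is not generally lost.** A reader might infer that the early visits dilute a growing effect, since the average carries only (1/3 + 2/3 + 1)/3 = 67% of the Week 12 interaction. But the average is also less variable (SD 3.57 against 4.9 kg): 0.667/3.57 = 0.19 per kg against 1/4.9 = 0.20. Linear growth costs almost nothing, and for a constant interaction the averaged term is stronger.
- **The three-way term is not useless.** A reader might infer that spreading over 6 df (12 for cancer type) makes it weak. For an interaction confined to Week 12 it has power 0.44 against 0.27, and it is already among the planned p-values. What it cannot say is whether the Week 12 effects differ.
- **The consequence is limited.** No decision rule uses these unadjusted p-values, the tables cover every visit, and Week 12 differences with 90% CIs are produced regardless, as is a plot of GDF-15 against Week 12 change.

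All four stand as limits on the size of the problem. None supplies a test of the Week 12 interaction.

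**Conclusion.** The point holds as a mismatch between question and test. If the p-values are overall Type III term tests, none of them tests whether the Week 12 treatment effect differs by cancer type, platinum use or GDF-15, and they can disagree with the Week 12 estimates in both directions. The algebra does not depend on any assumed variance. The power figures do: visit SDs, correlations and the subgroup split are assumptions, and they serve only to show that the disagreement can be material.

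The documents do not support reading this as a uniform loss of power, or as a prediction that readers will be misled about who benefits. They could be, in analyses that are supportive and where even the right contrast has power of only about 0.27 for a 2.7 kg interaction. Nor does the defect require withholding the term-level tests or adding a separate 400 mg contrast. This is a minor but worthwhile correction.

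**What to change.** In SAP 6.5, replace the sentence on interaction p-values. For each factor, report as the interaction test the Week 12 treatment-by-subgroup contrast from the same MMRM: 3 df for platinum use and dichotomized GDF-15, 6 df for cancer type. Beside it, give 90% CIs for the between-subgroup difference in each dose-versus-placebo effect at Week 12, naming the pairs of cancer types compared. If the term-level p-values are kept, label subgroup-by-treatment as the average over Weeks 4, 8 and 12, and the three-way term as change in the interaction over time. State the test type.

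The cost is one contrast statement per subgroup model. The model, data and analysis set do not change.

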6.6. Baseline and Other Summaries and Analyses

6.6.1. Baseline Summaries

Demographic data, concomitant medications, GDF-15 concentrations (at screening, using the Roche Elecsys assay), height, weight, BMI, ECOG PS (at screening). LSMI, sarcopenia status and BMI-adjusted weight loss category will be summarized, as defined in Section 5.2.1 or 5.2.2, as appropriate.

In addition, a subset of medical history data will be reported; this will include type and stage of cancer, TNM stage, the extent of the cancer (e.g metastatic vs non-metastatic; location of metastatic disease), the time from cancer diagnosis to randomization, and the percent weight loss in the 6 months prior to screening, where feasible. Cancer therapy details will also be summarized, as defined in Section 5.2.1 or 5.2.2, as appropriate, including line and type of prior cancer therapy, type and intent of current cancer therapy and whether participants are currently receiving no cancer treatment, or cancer treatment with or without platinum-based chemotherapy (both at randomization [+/- 28 days] and during treatment phase) and whether surgery or radiation was part of this cancer treatment.

Baseline inflammation will also be summarized, as defined in Section 5.2.1 or 5.2.2, as appropriate, including CRP, albumin, CRP-albumin ratio, modified Glasgow Prognostic Score, NLR and PLR.

The above baseline summaries will also be produced separately for the PK substudy only but may be reported in a supplemental CSR rather than the main CSR.

Other data collected at Screening that are used for inclusion/exclusion criteria, such as laboratory data, will be considered source data, and will not be required to be reported, unless otherwise noted.

6.6.2. Study Conduct and Participant Disposition

Participant evaluation groups will show participant disposition for each phase of Part A of the study (screening, treatment and follow-up for participants not continuing to Part B of the study). They will additionally show which participants were analyzed for efficacy, PK, PD, immunogenicity as well as for safety. Frequency counts and percentages will be supplied for

participant discontinuation(s) by treatment group and overall. Data will be reported in accordance with the sponsor reporting standards.

6.6.3. Concomitant Medications and Nondrug Treatments/Procedures

All prior and concomitant medication(s) as well as non-drug treatment(s)/procedure(s) will be reported according to current sponsor reporting standards.

Additionally, any actions taken with participants' anti-cancer therapy (e.g. discontinuation or dose-reduction) during the study will be summarized descriptively by treatment group, as defined in Section 5.2.2.

6.6.4. Treatment Compliance

A summary table of treatment compliance will be produced according to current sponsor reporting standards.

6.6.5. Retained Research Samples

Pharmacogenomic or biomarker data from Retained Research Samples may be collected during or after the trial and retained for future analyses; the results of such analyses (other than CRP, as described in Section 3.5) are not planned to be included in the CSR.

6.6.6. Population PK

As permitted by data, and determined by the sponsor, the PK/PD relationship between serum ponsegromab concentration and the effect on primary, secondary and/or tertiary endpoints may be explored using a population PK/PD approach. The population PK/PD analysis, if conducted, will be reported in a separate report.

7. INTERIM ANALYSES

7.1. Introduction

Interim analyses may be performed to assess efficacy and/or safety after at least approximately 25% of the planned participants, ie, approximately 30 participants, complete their study participation through Week 12 of the study. Interim analysis results may be used for decisions regarding stopping for futility, stopping for early success, conducting a sample size re-estimation, or adapting the study after the interim analysis. Participants may be discontinued from the study intervention/study as a result of the interim analysis, as described in the protocol.

Before any interim analysis is performed, the details of the objectives, decision criteria, dissemination plan, and method of maintaining the study blind (if applicable) as per Pfizer's SOPs will be documented and approved in an IRC charter.

In addition, ongoing monitoring of the safety of participants will be performed by an IRC. Further details are provided in Section 10.1.5.1 of the protocol and will be further documented in an IRC charter.

Following completion of Part A (PCD), the data will be analyzed and reported in the CSR. The results for Part B will be reported separately at the end of Part B.

7.2. Interim Analyses and Summaries

An interim analysis may be conducted after approximately 50% of randomized participants reach the Week 12 visit in Part A or discontinue the study prior to that visit.

The participants to be included in the interim analysis are:

Interim Population	Description
Interim Safety Population	All participants randomized prior to the date of data snapshot.
Interim Efficacy Population	Participants who were randomized up to 11SEP2023

All interim analyses will be carried out using the relevant Analysis Set (as defined in Section 4) applied to the Interim Populations described above.

7.2.1. Efficacy Endpoints

For **body weight**, the descriptive summaries and main statistical analyses, described in Section 6.1.1.1, will be performed. Additionally, Bayesian predictive probabilities will be calculated, separately for each dose versus placebo, for end of study success based on both the MMRM results at Week 12 and the primary Bayesian E_{max} model results. The predictive probabilities will be calculated using the method described by Grieve (1991)³, incorporating vague priors. Additionally, the subset summary tables by tumor type, as described in Section 6.5, will be produced.

For digital endpoints (gait speed, 95th percentile gait speed, MVPA and sedentary activity time), PROs (FAACT-ACS, FAACT-5IASS, CRCSD-appetite, CRCSD-fatigue, PROMIS-fatigue and PROMIS-physical function) and LSMI, the descriptive summaries and statistical analyses, described in Sections 6.2.1, 6.2.2, 6.2.3, 6.4.6, 6.4.7 and 6.4.10, will be performed. Additionally, Bayesian predictive probabilities will be calculated, separately for each dose versus placebo, using the method described by Grieve (1991)³, incorporating vague priors, for end of study statistical significance based on the MMRM/ANCOVA results at Week 12.

Additionally, the overall tumor response according to RECIST guidelines will be summarized as described in Section 6.4.9.

7.2.2. Safety Endpoints

Adverse events, laboratory abnormalities, vital signs and ECG abnormalities will be summarized and analyzed as described in Section 6.2.4. A subset of these outputs, previously agreed with the C3651003 IRC, will be produced.

7.2.3. Other Summaries

[figure not shown]
Baseline summaries will be produced, as described in Section 6.6.1, for both the interim Safety and Efficacy populations.

[figure not shown]

Appendix 1. FAACT Scoring Guidelines

*For guidelines on handling missing data and scoring options, please refer to the Administration and Scoring Guidelines in the manual or on-line at www.facit.org.

Appendix 2. Sampson Criteria

Clinical Criteria for Diagnosing Anaphylaxis

Anaphylaxis is highly likely when any one of the following 3 criteria are fulfilled:

- Acute onset of an illness (minutes to several hours) with involvement of the skin, mucosal tissue, or both (eg, generalized hives, pruritus or flushing, swollen lips-tongue-uvula)
 - AND AT LEAST ONE OF THE FOLLOWING
 - a. Respiratory compromise (eg, dyspnea, wheeze-bronchospasm, stridor, reduced PEF, hypoxemia)
 - b. Reduced BP or associated symptoms of end-organ dysfunction (eg, hypotonia [collapse], syncope, incontinence)
- 2. Two or more of the following that occur rapidly after exposure to a likely allergen for that patient (minutes to several hours):
 - a. Involvement of the skin-mucosal tissue (eg. generalized hives, itch-flush, swollen lips-tongue-uvula)
 - b. Respiratory compromise (eg, dyspnea, wheeze-bronchospasm, stridor, reduced PEF, hypoxemia)
 - c. Reduced BP or associated symptoms (eg, hypotonia [collapse], syncope, incontinence)
 - d. Persistent gastrointestinal symptoms (eg, crampy abdominal pain, vomiting)
- 3. Reduced BP after exposure to known allergen for that patient (minutes to several hours):
 - a. Infants and children: low systolic BP (age specific) or greater than 30% decrease in systolic BP*
 - b. Adults: systolic BP of less than 90 mm Hg or greater than 30% decrease from that person's baseline

PEF, Peak expiratory flow; BP, blood pressure.

Programmatically Identifying Potential Cases of Anaphylaxis

A participant is said to have an episode fulfilling the Sampson Criteria if at least one of the following criteria is met:

- **Criterion 1:** The participant experienced an onset of both Condition 1 and Condition 2 below, on the day of, or on the day after, study drug administration.
 - a) Condition 1: a skin or mucosal membrane adverse event (AE) (using MedDRA PTs under Skin or Mucosal Membrane grouping),
 - b) Condition 2: a respiratory compromise AE (using MedDRA PTs under the Respiratory grouping), or an end-organ dysfunction/reduced blood pressure AE (using MedDRA PTs under End-organ dysfunction or Reduced Blood Pressure grouping), or reduced systolic blood pressure (characterized by a PT of hypotension, blood pressure decreased or blood pressure systolic decreased).
- **Criterion 2:** The participant experienced an onset of any 2 or more conditions below, on the day of, or on the day after, study drug administration.
 - a) Condition 1: a skin or mucous membrane involvement AE (using MedDRA PTs under Skin or Mucosal Membrane grouping)
 - b) Condition 2: a respiratory compromise AE (using MedDRA PTs under the Respiratory grouping);

^{*}Low systolic blood pressure for children is defined as less than 70 mm Hg from 1 month to 1 year, less than (70 mm Hg + [2 × age]) from 1 to 10 years, and less than 90 mm Hg from 11 to 17 years.

[figure not shown]
- c) Condition 3: an end-organ dysfunction/reduced blood pressure AE (using MedDRA PTs under 'End-Organ Dysfunction or Reduced Blood Pressure grouping), or reduced systolic blood pressure (characterized by a PT of hypotension, blood pressure decreased or blood pressure systolic decreased);
- d) Condition 4: a gastrointestinal AE (using MedDRA PTs under the gastrointestinal grouping).

If the same specific AE belongs to more than one Condition/AE grouping above (i.e., 'Skin or Mucosal Membrane' grouping, 'Respiratory Compromise' grouping, 'End-Organ Dysfunction/ Reduced Blood Pressure' grouping, 'Gastrointestinal' grouping), the event should be assigned to not more than one of the above Conditions and in such a way as to maximize the number of Conditions fulfilled to support Criterion 2. For example, if the AE of Dyspnea (which belongs to the 'Respiratory Compromise' grouping) and the AE of Chest Pain (which may belong either to the 'Respiratory Compromise' grouping or to the 'End-Organ Dysfunction/ Reduced Blood Pressure' grouping, Reduced Blood Pressure' grouping, so that Criterion 2 is fulfilled (if the AE of Chest Pain were assigned to the 'Respiratory Compromise' grouping, then Criterion 2 would not be fulfilled because the AE of Dyspnea also belongs to the 'Respiratory Compromise' grouping).

- Criterion 3: The participant experienced reduced systolic blood pressure (characterized by a PT of hypotension, blood pressure decreased or blood pressure systolic decreased) on the day of, or on the day after, study drug administration, and at least 1 qualifying event. A qualifying event is defined as anv of the following occurring during the current study or, if applicable, in the parent study from which the participant rolled over into the current study, after the first administration of the study drug (in the current or the parent study, as applicable) and before the administration of the same study drug associated with the current reduced systolic blood pressure event:
 - a) An event meeting Criterion 1 or Criterion 2;
 - b) An Injection Site reaction (ISR), as reported by the investigator;
 - c) An AE under the Anaphylactic Reaction Standardised MedDRA Query (SMQ), or the Angioedema SMQ, or the Hypersensitivity SMQ, considered to be related to the study drug, as reported by the investigator.

For episodes with multiple AEs fulfilling more than one Sampson Criteria at the same visit, the following hierarchy is used: Criterion 1, Criterion 2, Criterion 3. For example, when Criterion 1 is fulfilled, Criterion 2 and Criterion 3 are not evaluated.

